**Abstract:**

Background: High-resolution, relational, resonance-based, electroencephalic mirroring (HIRREM®) is a closed-loop, allostatic, acoustic stimulation neurotechnology that uses software-guided algorithmic analysis to identify and translate selected brain frequencies into audible tones to support real-time self-optimization of brain activity. Prior research demonstrates that the use of HIRREM is associated with reduced symptoms of insomnia, and traumatic stress and anxiety, and improved autonomic cardiovascular regulation across heterogeneous cohorts. HIRREM has been safe and well tolerated in about 500 people across six IRB-approved studies. However, the current in-office HIRREM approach remains very operator dependent (extensive Technologist education and experience) and takes a sizeable time commitment from the participant (typically ten to twenty sessions of 90-120 minutes each). To reduce participant time required, and operator dependence, while increasing scalability, a new generation of hardware and software has been developed. Based on the same core technology and algorithms to mirror brainwaves with audible tones, this now includes the use of faster, 64-bit processing architecture for faster feedback, the use of 4 sensors, and the use of a standard series of protocols, all done with eyes closed (HIRREM Standard Operating Procedure, HIRREM-SOP). Although only 2 sensors are active at a time, applying 4 sensors, for which the software can switch from one pair to the other automatically, cuts in half the number of sensor placement changes needed, with reduced session time and interruptions. The placebo condition has also been modified so there is randomness to both the pitch and the timing of the tones, using tones that have not been acoustically engineered. This pilot study will evaluate feasibility and effects of this standardized, fixed dose, enhanced approach, and the effectiveness of blinding for the placebo condition in participants with symptoms of insomnia.

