**Objectives:**

The primary objective of this randomized pilot study is to evaluate the effect of 10 sessions of standardized acoustic stimulation linked to brain activity (HIRREM-SOP), compared to 10 sessions of nonspecific acoustic stimulation not linked to brain activity (randomly generated tones), on symptoms of insomnia, based on change in ISI score from V1 to V3. The secondary objective is to evaluate the effectiveness of blinding for the placebo condition based on the expectation measure regarding group assignment prior to the 5th session. Tertiary, exploratory objectives include evaluation of the effects on other symptom and physiological measures.

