**Importance:**

This study will explore the use of HIRREM-SOP for insomnia, in a randomized, controlled pilot clinical trial. Results will provide important insights regarding the effect of a new generation of this novel closed-loop, acoustic stimulation, applied using a standardized protocol and a fixed number of sessions. This, in a population shown to benefit from use of the legacy technology. It will confirm feasibility of use for the upgraded technology in this population, provide estimates of effect size, and assess effectiveness of blinding for a modified placebo control condition. All will be useful for planning future controlled trials. Although not anticipated with this small pilot trial, a positive result would suggest that HIRREM-SOP might have benefit as a noninvasive, non-drug alternative for initial management of sleep trouble. The study may also help to identify characteristics of subgroups that may experience differential effects/benefits from HIRREM-SOP.

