Since 2011, the HIRREM Research Program at WFSM has enrolled almost 500 participants in six IRB-approved clinical studies to evaluate the effects and potential benefits of HIRREM. Use of HIRREM has been associated with reduced sleep symptomatology and reduced high frequency amplitudes in adults with insomnia [23], reduced menopausal symptoms in women [24], improved sleep in athletes with persisting post-concussion symptoms [25], reduced symptoms, and temporal lobe high frequency asymmetry in self-reported post-traumatic stress [26], and reduced symptoms of military-related traumatic stress [26]. Improved autonomic cardiovascular regulation has also been observed in those receiving HIRREM, including a cohort of adolescents with Postural Orthostatic Tachycardia Syndrome [27]. In addition, correlation has been reported between high frequency electrical brain pattern asymmetry scores at baseline, and measures of autonomic cardiovascular regulation [28].

In addition, a placebo controlled efficacy trial of in-office HIRREM for moderate to severe insomnia demonstrated a clinically meaningful reduction of insomnia symptoms ( $\geq 7$  point reduction on the ISI), and statistically significant additional benefit associated with use of HIRREM, as compared to a sham placebo of random audible tones not linked to brainwaves [29]. HIRREM was well tolerated, and the benefit was durable through the final follow up visit, 4 months after completion of the intervention (Figure 1).

Continuous recording (10 minutes) of blood pressure and heart rate also allowed for analysis of autonomic cardiovascular regulation, including multiple measures of heart rate variability and baroreflex sensitivity. Data were obtained at all study visits. Analysis demonstrated significant improvement in multiple objective measures of autonomic cardiovascular regulation including increased baroreflex sensitivity (HF $\alpha$ , and Sequence ALL) and heart rate variability (SDNN, and rMSSD), associated with this short term use of in-office HIRREM, compared to a placebo intervention of random audible tones not linked to brainwaves (Figure 2). The benefit was seen at all follow up data collections, and was durable through the final follow up at 4 months post-intervention [30]. There was no significant improvement seen in the placebo group at any time point. It is not clear whether these results reflect a cause, an effect, or both relative to the observed improvement of insomnia symptoms.

Figure 1:

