### New Developments:

The in-office HIRREM approach used for research since 2011 remains very operator dependent (extensive Technologist education and experience required), and requires a lot of time for sessions (typically 10-20 sessions of 90-120 minutes each). To reduce the length of sessions, and reduce operator dependence, while increasing scalability, a new generation of hardware and software has been developed. Although based on the same core technology and algorithms for rapidly mirroring brainwaves back as audible tones in a closed-loop paradigm, the improved device includes the use of faster, 64-bit processing architecture for faster feedback, the use of 4 sensors, and the use of a standard series of protocols, all done with eyes closed (HIRREM-SOP). Although only 2 sensors are active at one time, the Technologist can apply 4 sensors at the same time. The software can switch from one pair to the other automatically, which effectively cuts in half the number of sensor placement changes needed during a session, yielding a shorter session time with fewer interruptions.

Informed by experience with prior controlled trials, the placebo condition has also been modified. The modified approach includes intentional randomness to both the pitch of the tones, as well as the timing and occurrence of the tones. In addition, characteristics of the tones themselves are not acoustically engineered. This appears to hold great promise as an improved placebo condition for use as a control in research evaluating this intervention.

This pilot study will evaluate feasibility of using this standardized, enhanced approach with HIRREM-SOP, and the effectiveness of the blinding for the placebo condition, in participants with symptoms of insomnia.

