### Research Design and Method:

#### Objectives:

##### Primary Objective:

The primary objective of this randomized pilot study is to evaluate the effect of 10 sessions of standardized acoustic stimulation linked to brain activity (HIRREM-SOP, BCC), compared to 10 sessions of nonspecific acoustic stimulation not linked to brain activity (randomly generated, nonspecific tones, NCC), in addition to continued current care, on symptoms of insomnia, based on change in ISI score from V1 to V3.

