##### Tertiary/Exploratory Objectives:

Evaluate whether the addition of acoustic stimulation linked to brainwaves (BCC group), as compared to the addition of nonspecific acoustic stimulation not linked to brainwaves (NCC group), to continued current care, will result in greater differential changes in a variety of physiological, and behavioral outcome measures outlined below.

1. Autonomic nervous system functions, as manifested by heart rate, HRV, and BRS. We expect to see greater changes in autonomic activity and an improvement of sympatho-vagal balance in the BCC group. This would be reflected as changes in heart rate, and an increase of HRV and BRS parameters such as the standard deviation of the R-R interval (SDNN), rMSSD, HF alpha, and Sequence Up, Down, or All.
2. Additional behavioral outcomes such as insomnia (assessed by the Pittsburgh Sleep Quality Index, PSQI; and the Epworth Sleepiness Score, ESS), depression (as assessed by the Center for Epidemiological Studies-Depression Scale, CES-D), anxiety (as evaluated by the GAD-7), and stress (as assessed by the Perceived Stress Scale, PSS). We expect to see greater improvement in these symptom inventory scores in the BCC group.

Overview:

This will be a single site, single blind, placebo controlled, pilot clinical trial, enrolling adults who have insomnia. Assuming a potential dropout rate of 20%, up to 24 subjects will be enrolled to achieve a target of 20 subjects (10 per group) that complete the study. Subjects aged 18 or older, with symptoms of at least mild insomnia as defined by either subthreshold, moderate, or severe clinical insomnia by the Insomnia Severity Index (ISI  $\geq 8$ ), not attributable to another known cause (e.g. obstructive sleep apnea, restless legs syndrome, benign prostatic hypertrophy), will be randomly assigned to receive 10 sessions of acoustic stimulation linked to brain activity over 4 weeks (BCC), or 10 sessions of acoustic stimulation not linked to brain activity over 4 weeks (NCC). Sessions will be 1-1.5 hours in length. Both groups will continue their other usual care throughout.

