Individuals assigned to the nonspecific acoustic stimulation group (NCC) will undergo sessions that mimic HIRREM-SOP in all appearances and procedures, including behaviors and subjective intentionality of the Technologist, and the number and scalp locations of protocols delivered during each session. However, in place of acoustic stimulation consisting of tones that vary in pitch and timing based on algorithmic analysis of real time brain activity, participants assigned to the NCC group will receive tones generated by a random signal generator. This includes randomness for both the timing, and the pitch of the tones, which are also not acoustically engineered. Technologists will be specifically instructed and trained to maintain comparable mental and behavioral interactional styles with all participants, both to minimize or eliminate confounding effects of Technologist subjectivity on differential outcomes associated with BCC and NCC groups, and to maintain subject blinding.

Safety:

Based on experience reported by Brain State Technologies, garnered from provision of case management support, feedback from their clients, and feedback from the HIRREM provider community, as well as results from IRB-approved studies at WFSM (now about 500 participants who have received HIRREM), the study team is not aware of any serious adverse events resulting from HIRREM sessions.

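### Does describing the placebo tones as not acoustically engineered undermine what the V1-to-V3 ISI contrast estimates?

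*Combined protocol and SAP*

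**What the plan says.** The placebo's tone character appears in three places.

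- Non-specific acoustic stimulation (the intervention section): the tones come from a random signal generator. "This includes randomness for both the timing, and the pitch of the tones, which are also not acoustically engineered".
- Abstract, Background: the modified placebo has "randomness to both the pitch and the timing of the tones, using tones that have not been acoustically engineered".
- New Developments: random pitch and timing are given first, then "In addition, characteristics of the tones themselves are not acoustically engineered".

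The objectives use shorter labels. The Abstract's Objectives set HIRREM-SOP against "nonspecific acoustic stimulation not linked to brain activity (randomly generated tones"). The Primary Objective sets it against "nonspecific acoustic stimulation not linked to brain activity (randomly generated, nonspecific tones, NCC"). The Tertiary/Exploratory Objectives ask "whether the addition of acoustic stimulation linked to brainwaves (BCC group), as compared to the addition of nonspecific acoustic stimulation not linked to brainwaves".

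Two further places bear on the reading. Relevant Pilot Data describes the earlier insomnia trial's benefit "as compared to a sham placebo of random audible tones not linked to brainwaves". The Importance section says this pilot will "provide estimates of effect size, and assess effectiveness of blinding for a modified placebo control condition".

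The primary test, under Sample Size and Statistical Analysis, is a between-group mean contrast in ISI change from V1 to V3 from a linear mixed model, with a target of 10 completers per group.

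**The concern.** In the intervention section and in New Developments, the wording presents the lack of acoustic engineering as something added to random pitch and timing. That suggests the active tones are engineered, so the arms would differ in two ways: whether the tones follow the brain, and what the tones are like. The objectives mention only the first, beyond saying that the tones are randomly generated.

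A reader who takes the objectives literally could treat the ISI difference as the effect of brain linkage. Because the pilot is meant to supply effect sizes for later trials, that reading could be carried to a trial with a different unlinked placebo. The label invites this a little, since the earlier trial's placebo was also described as random tones not linked to brainwaves, although the placebo has since been changed. The paragraph explaining the fixed protocol set adds to the worry, because it speaks of pinning down what the software contributes.

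**Working it through.** The plan gives no effect size, standard deviation, alpha or power for this comparison and says there were no data for a formal sample size. There is therefore no stated figure to reproduce. The check is one of identifiability, followed by a reading of the text.

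**1. What the two arms can estimate.** Let L be the effect of brain linkage on ISI change, T the effect of engineered tones and I any interaction. Let e = 1 if the active tones are engineered and e = 0 if not. The documents do not give e.

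- NCC mean change: μ
- BCC mean change: μ + L + e(T + I)
- Difference: Δ = L + e(T + I)

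If e = 0, then Δ = L and nothing is confounded.

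If e = 1, then Δ = L + T + I. Leaving the interaction aside, the design rows for (intercept, linkage, tone) are (1,1,1) for BCC and (1,0,0) for NCC. The rank is 2 for 3 parameters, so only the sum L + T is estimable. Repeating these rows 10 times per group, or any number of times, leaves the rank at 2.

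**2. Bias for the comparison that is planned.** The target is HIRREM-SOP against this placebo, which is Δ itself. Randomisation gives a bias from this source of Δ − Δ = 0, whether e is 0 or 1.

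**3. Whether the crossover helps.** NCC participants who cross over move to brain-linked sessions, so linkage and tone character would change together. The crossover does not separate them.

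**4. Whether the text claims more than Δ.**

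| Place | What it supports |
|---|---|
| Abstract Objectives; Primary Objective | Names HIRREM-SOP as the intervention and randomly generated tones as the comparator: treatment against placebo |
| Non-specific acoustic stimulation | Describes the placebo in full, including tone character |
| Importance | Promises effect sizes and, in the same sentence, calls the placebo modified |
| Background | Says the mechanism is not yet fully understood |
| HIRREM-SOP description | Justifies a fixed protocol set mainly as a way to limit Technologist judgment |

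None of these states that a difference will be credited to linkage alone.

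**5. What a design change would do.** A third arm with engineered but unlinked tones raises the rank to 3 of 3. A two-arm design with tone character matched would isolate L. Either answers a different question. Replacing the placebo would also remove the condition whose blinding is the secondary objective.

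**The case for a change.** The strongest case for acting is that the objectives are what readers carry into a report or the next trial, and they leave out a feature the protocol itself treats as distinct. The inference that the active tones are engineered is reasonable. Listing the lack of engineering as a mark of the modified placebo would serve little purpose if both arms shared it, and the HIRREM-SOP description calls the reflected tones musical. The cost would be a few sentences, and the tone character of one arm is given while that of the other is not.

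Much of this stands as description. The omission is real, and if the inference is right the two features cannot be separated. What does not stand is the step to a needed change. A short label in the objectives with the detail in the intervention section is ordinary protocol structure. The objectives are not worded by linkage alone, since the first two name the HIRREM-SOP system and randomly generated tones; the exploratory objectives come closest to it. The labels for the earlier and present placebos overlap but are not identical, and the protocol says more than once that the placebo was modified. Leaving components unseparated is inherent in comparing a whole intervention with a sham, and is a fair choice for a pilot seeking 20 completers.

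**Conclusion.** No change is needed. Provided the active tones are engineered, which the documents imply but do not state, the V1-to-V3 ISI contrast estimates HIRREM-SOP as delivered against this modified placebo and cannot split linkage from tone character. If they are not engineered, the question disappears. In both cases the bias for the planned comparison from this source is zero, and the placebo, sample size, endpoint and analysis are unaffected.

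What remains is a gap in description that an analyst would fill sensibly by reporting the result as HIRREM-SOP against random, non-engineered tones. The authors may, if they wish, state the tone character of both arms and note that a difference reflects that comparison and not brain linkage by itself. No result depends on it.

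This conclusion rests on reading the primary objective as intervention against placebo, which its wording supports. It would need revisiting if a report credited the difference to brain linkage alone.

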**Data and Safety Monitoring:**

The principal investigator will be responsible for the overall monitoring of the data and safety of study participants. The principal investigator will be assisted by other members of the study staff.

Any collected patient identifying information corresponding to the unique study identifier will be maintained on a separate master log. The master log will be kept secure, with access limited to designated study personnel. Following data collection subject identifying information will be destroyed at the earliest opportunity, consistent with data validation and study design, producing an anonymous analytical data set. Data access will be limited to study staff. Data and records will be kept locked and secured, with any computer data password protected.

**Reporting of Unanticipated Problems, Adverse Events, or Deviations:**

Any unanticipated problems, serious and unexpected adverse events, deviations or protocol changes will be promptly reported by the principal investigator or designated member of the research team to the IRB and sponsor or appropriate government agency if appropriate.

